7.3. Unscheduled Visits

If, during the investigation a symptomatic subject requires an unscheduled visit to the clinical site, the following information will be collected at a minimum (if applicable):

- Chief complaint prompting the visit. If the reason is an adverse event, the applicable eCRF for the adverse event must be completed and subject record completed as appropriate
- Date and time of the visit and all procedures completed at the unscheduled visit
- Review of adverse event and concomitant medications
- Documentation of any test article dispensed or collected from the subject, if applicable
- Slit lamp findings (using the Slit Lamp Classification Scale)

If the Investigator withdraws a subject from the study, the final study visit case report forms must be completed indicating the reason(s) why the subject was withdrawn. The subject record must be completed documenting the date and primary reason for withdrawal and the study CRA notified.

Any ocular and non-ocular Adverse Events that are ongoing at the time of the study visit will be followed by the Investigator, within licensure, until they have resolved, returned to pre-treatment status, stabilized, or been satisfactorily explained. If further treatment i.e., beyond licensure is required, the subject will be referred to the appropriate health care provider.

The following information will be collected during an unscheduled visit. The investigational sites only need to complete steps U.1, U.2, and U.6 for asymptomatic subjects that simply require a replacement lens.

ñ.	Unscheduled Visit			
Step	Procedure	Details		
U.1	Chief Complaints	Record the subject's chief complaints for reasons for the unscheduled visit.		
U.2	Adverse Events and Concomitant Medications Review	Review any changes to the subject's medical history or concomitant medications from the previous study visit. Record any changes, and any adverse events.		
U.3	Entrance VA	Record the entrance distance visual acuity (OD, OS and OU) to the nearest letter.		

1	Unscheduled Visit				
Step	Step Procedure Details				
U.4	Subjective Sphero- cylindrical Refraction	The investigator will complete a subjective refraction (sphere and cylinder) and record the resultant distance visual acuity OD, OS, and OU to the nearest letter.			
U.5	Slit Lamp Biomicroscopy	FDA Slit Lamp Classification Scale will be used to grade the findings. If the clearance of the fluorescein needs to be expedited, preservative-free rewetting drops may be instilled.			
U.6	Dispensing (if applicable)	Additional lenses may be dispensed if one is lost or torn during the wearing period.			
U.7	Exit Visual Acuity	Record the subject's exit distance visual acuity (OD, OS, and OU) to the nearest letter.			

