14. STATISTICAL METHODS

14.1. General Considerations

Statistical Analysis will be undertaken by the sponsor or under the authority of the sponsor. A general description of the statistical methods to be implemented in this clinical trial is outlined below. More details will be included in the stand-alone Statistical Analysis Plan (SAP). The SAP will be developed and finalized prior to database lock.

All data summaries and statistical analyses will be performed using the SAS software Version 9.4 or higher (SAS Institute, Cary, NC). Throughout the analysis of data, the results for each subject/eye will be used when available for summarization and statistical analysis. Unscheduled visits will be summarized separately and will be excluded from the statistical analysis.

Summary tables (descriptive statistics and/or frequency tables) will be provided for all baseline variables, efficacy variables and safety variables as appropriate. Continuous variables will be summarized with descriptive statistics (n, mean, standard deviation [SD], median, minimum and maximum). Frequency count and percentage of subjects or eyes within each category will be provided for categorical data.

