## 1. INTRODUCTION

This statistical analysis plan (SAP) describes the analyses and data presentations for protocol CR-6305 Version 4.0 Amendment 3.0.

This document will serve as the final guidance for all the statistical analysis for this study and will supersede the Statistical Method section in the protocol if there are any discrepancies. Any deviation from the analysis plan will be documented as such in the clinical study report.

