## Slit Lamp Findings (Grade 3 or Higher)

Slit Lamp Findings will be assessed for each subject eye at all study visits (schedule and unscheduled). SLF is a binary response where Y=1 for at least one Grade 3 or 4 slit lamp finding. The percentage of eyes with Grade 3 or higher slit lamp findings will be analyzed and will include corneal infiltrates. Eyes with multiple events will be counted only once.

The FDA Biomicroscopy Scale measures the severity of the ocular clinical findings and goes from Grade 0 (none) to Grade 4 (severe). The procedure is explained in the section 12 Appendix D of the study protocol. The individual ocular finding results are considered as other endpoints.

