## Fit Acceptance Rate

Acceptable lens fit will be assessed at all study visits (scheduled and unscheduled) for each subject eye. Fit acceptance rate will be based on the lens fit acceptance of eyes wearing the Test lens only. Fit acceptance is a binary response where Y=1 if lens fit is acceptable and Y=0 otherwise. Unacceptable is defined as unacceptable if any one of the following criteria:

- limbal exposure at primary gaze or with extreme eye movement;
- edge lift;
- excessive movement in primary up gaze;
- insufficient movement in all three of the following conditions: primary gaze, up gaze, and push up test.

Eyes with multiple unacceptable fitting events will be counted only once. Fit rates of the Control lens will also be collected but are not a primary endpoint.

The procedure is explained in the **section** in section 12 Appendix D of the study protocol. The individual lens fitting characteristics are considered as other endpoints.

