## 4. STATISTICAL HYPOTHESES FOR STUDY OBJECTIVES

#### 4.1. Primary Hypotheses

All the primary hypotheses must be met in order to satisfy the primary objective of this study.

- 1. Subjects wearing the JJVCI Investigational contact lenses on a daily wear basis will have patient reported comfort at the 2-Week Follow Up visit that is non-inferior to that of subjects wearing predicate device on a daily wear basis. A non-inferiority margin of -5 CLUE points will be used.
- 2. Subjects wearing the JJVC Investigational contact lenses on a daily wear basis will report distance monocular visual acuity (logMAR: bright room luminance / high contrast charts) at the 2-Week Follow Up visit that is non-inferior to that of subjects wearing predicate device on a daily wear basis. A non-inferiority margin of 0.05 LogMAR will be used.
- 3. Subjects wearing the JJVCI Investigational contact lenses on a daily wear basis will have patient reported outcome (Agree and Strongly Agree) on the Quality of Vision in Bright Light at the 2-Week Follow Up visit that is non-inferior to that of subjects wearing predicate device on a daily wear basis. A non-inferiority margin of 10% will be used.
- 4. Subjects wearing the JJVC Investigational contact lenses on a daily wear basis will have a percentage of any grade 3 or higher slit lamp findings at all visits (scheduled and unscheduled) that is non-inferior to that of subjects wearing predicate device on a daily wear basis. A non-inferiority margin of 5% will be used.
- 5. At least 90% of eyes wearing the JJVC Investigational contact lenses on a daily wear basis will have acceptable fits across the fitting and follow-up visits.

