#### 7.2. **Summary Statistics**

Throughout the analysis of data, the results for each subject/eye will be used when available for summarization and statistical analysis. Unscheduled visits will be summarized separately and will be excluded from the efficacy statistical analysis but will be included in the analysis of safety endpoints (slit lamp findings and lens fitting).

Summary tables (descriptive statistics and/or frequency tables) will be provided for all baseline variables, efficacy variables and safety variables as appropriate. Continuous variables will be summarized with descriptive statistics (n, mean, standard deviation [SD], median, minimum and maximum). Frequency count and percentage of subjects or eyes within each category will be provided for categorical data.

Safety variables will be summarized on both safety and PP populations whereas efficacy variables will be summarized on the PP and ITT populations.

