## **11.6.** Physical Examination Findings

Slit lamp findings will be assessed for each subject eye at baseline, the 2-week follow-up and at any unscheduled visit using the FDA Grading scale (Grade 0=None, Grade 1=Trace, Grade2=Mild, Grade 3=Moderate, Grade 4=Severe). Slit lamp finding assessments include the following metrics:

- Corneal Infiltrates (Yes/No)
- Corneal Edema
- Corneal Neovascularization
- Corneal Neovascularization Location
- Corneal Staining
- Corneal Staining Location
- Conjunctival Injection
- Tarsal Abnormalities
- Other

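### Lens fit and slit lamp findings are primary endpoints at every visit, but unscheduled visits and early exits have no fit assessment, so fit failures can go unrecorded in the Test lens's favour

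*Protocol*

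**What the plan says.** Both primary safety endpoints cover every visit. SAP 3.1 says of slit lamp findings: "Slit Lamp Findings will be assessed for each subject eye at all study visits (schedule and unscheduled"; and of fit: "Acceptable lens fit will be assessed at all study visits (scheduled and unscheduled) for each subject eye". Protocol 2.2 defines them the same way. An eye with any unacceptable fit, or any Grade 3 or 4 finding, counts once. SAP 7.2 states that unscheduled visits "will be included in the analysis of safety endpoints (slit lamp findings and lens fitting", and SAP 11.6 repeats the scope: "Slit lamp findings will be assessed for each subject eye at baseline, the 2-week follow-up and at any unscheduled visit".

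Protocol 14.1 says the reverse: "Unscheduled visits will be summarized separately and will be excluded from the statistical analysis". SAP section 1 settles precedence, since the SAP "will supersede the Statistical Method section in the protocol if there are any discrepancies".

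Protocol 7.3 sets out the unscheduled visit in seven steps: complaint (U.1), adverse event and medication review (U.2), entrance acuity (U.3), refraction (U.4), slit lamp (U.5), dispensing (U.6) and exit acuity (U.7). One group has a shorter list: "The investigational sites only need to complete steps U.1, U.2, and U.6 for asymptomatic subjects that simply require a replacement lens".

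Under Protocol 8.2 a discontinued subject completes the current visit and the Final Evaluation. Final Evaluation steps F.1 to F.3 are disposition, keratometry and refraction.

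**The concern.** All five primary hypotheses must be met, and two of them rest on these endpoints. Their definitions call for assessments that the visit procedures do not require. Missing values are not imputed (SAP 7.6), so an assessment that is not made adds no event.

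For fit this works in one direction. The criterion is single-arm, at least 90% of Test eyes, and an eye fails on any unacceptable assessment. Leaving out an assessment can only keep the acceptance rate the same or raise it. For slit lamp, a skipped examination can only lower the recorded event rate, in either arm, while the margin is a fixed 5 percentage points.

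At stake is whether the safety-population fit rate reflects subjects who leave because the lens fits badly. These are the failures the endpoint should count.

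**Working it through.** **Definitions against procedures**

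| Contact with the subject | Fit recorded? | Slit lamp recorded? |
|---|---|---|
| Visit 1 | Yes (1.22) | Yes, before lens fitting (1.12) |
| Unscheduled, symptomatic | No step | Yes (minimum list and U.5) |
| Unscheduled, asymptomatic replacement | No step | Not required (U.5 omitted) |
| Visit 2 | Yes (2.8) | Yes (2.12) |
| Final Evaluation F.1 to F.3 | No step | No step |

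**Following one subject**

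1. Step 1.24 allows dispensing only if fit is acceptable in both eyes, so every dispensed subject has two acceptable eyes on record.
2. The subject returns early and is discontinued for unsatisfactory fit, a listed reason in SAP 11.4.
3. The site completes the unscheduled visit and F.1 to F.3. Neither records fit.
4. The subject was administered a test article and has an observation, so stays in the safety population, on which fit is analysed (SAP 10.1).
5. The only fit values are the two acceptable ones from Visit 1. Two eyes count as successes.

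A misfit that is present between visits and gone by Visit 2 is lost in the same way.

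**Scale for fit**

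Inputs: 112 Test subjects, 224 eyes (Protocol 4.3); prior Beta(0.5, 0.5) (SAP 14.1, lens fit code); success if P(p > 0.90 | data) is at least 0.975 (SAP 10.1). With f failures among n units the posterior is Beta(0.5 + n − f, 0.5 + f). The two limiting cases for correlation between a subject's eyes give:

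- Eyes independent, n = 224: f = 14 gives 0.9752 (pass); f = 15 gives 0.956 (fail); f = 16 gives 0.928 (fail).
- Eyes fully correlated, n = 112 subjects: f = 5 gives 0.983 (pass); f = 6 gives 0.9585 (fail).

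With the 116 per arm planned for randomisation, the tolerances are still 14 (of 232 eyes) and 5 (of 116 subjects).

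One unrecorded bilateral failure raises the observed rate by 2/224 = 0.9 percentage points. It reverses the result only if the recorded failures already stand at 13 or 14 eyes in the independent case, or at 5 subjects in the fully correlated case.

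**Slit lamp**

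If a share m of Grade 3 or higher findings is missed equally in both arms (an assumption; no value is available), the observed difference is (1 − m)(pT − pC). Any true excess shrinks against the 5-point margin. The documents give nothing from which to set m.

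**The case against.** The case against is substantial, and much of it stands.

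- **Computability.** A reader might infer that the fit endpoint cannot be computed as defined. That goes too far. Fit is required at Visits 1 and 2, each eye is scored once, and every completer has a value. What is incomplete is capture between visits and at early exit.
- **Slit lamp.** A reader might infer that any replacement visit may skip the slit lamp. Protocol 7.3 limits this to asymptomatic subjects who need only a replacement, and symptomatic visits require it. Protocol 13.1 lists other Grade 3 or higher corneal findings among events that usually cause symptoms. What can be lost is a silent finding that has gone by Visit 2.
- **Likelihood of misfit.** It is tempting to say that unscheduled visits are where misfit is most likely. The documents do not support this: the stated replacement triggers are loss, damage or tearing, and the pooled historical studies report no unacceptable fits.
- **Other safety nets.** A replacement lens has the same nominal base curve and diameter, so a persistent misfit should still show at Visit 2. Discontinuation and replacement reasons are tabulated. These help, but neither tabulation feeds the primary endpoint, and subjects who leave early have no Visit 2.
- **Hypothesis 5.** Its wording, "will have acceptable fits across the fitting and follow-up visits", might be read as excluding unscheduled visits. Protocol 4.1 and SAP 2.1 call those visits unscheduled follow-up visits, so this conflict is weak.
- **Power figures.** The n = 100 exact test behind the sample size passes with probability 44% at a true 95% rate and 82% at 97%. Those rates are assumptions, that test is not the planned analysis, and neither figure measures the effect of a missing assessment.

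**Conclusion.** The mismatch is real and its direction for fit is certain: missing assessments can only hold or raise the Test acceptance rate. The clearest route is early discontinuation for poor fit, where the subject remains in the analysis as two acceptable eyes. The slit lamp gap is narrower, confined to asymptomatic replacement visits.

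The size cannot be computed. No unscheduled-visit rate is given, and with no unacceptable fits and no Grade 3 or higher findings in the historical studies the effect may well be nil. The tolerance of 14 eyes or 5 subjects rests on 112 Test subjects, the SAP prior and the two limiting correlations, and shows only that one or two unrecorded subjects matter near the boundary.

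This is a cheap improvement that should be made, because it removes a one-sided bias from a primary endpoint. It does not invalidate the endpoint.

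**What to change.** 1. Add the existing acceptable/unacceptable fit item, by eye and before lens removal, to the symptomatic unscheduled-visit form and to the early-discontinuation evaluation when the lens is still worn.
2. State in the SAP that an eye discontinued for unsatisfactory lens fitting counts as a fit failure. SAP 11.4 counts discontinuations by subject, so the rule must also say how a subject's reason is assigned to eyes.
3. Restate both endpoints, in the same words in both documents, as scheduled visits plus unscheduled visits at which the assessment was made. This covers asymptomatic replacement visits, which item 1 leaves without either assessment, and clarifies hypothesis 5.
4. Reconcile Protocol 14.1, which excludes unscheduled visits from analysis, with SAP 7.2, which includes them for safety.

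Cost: about a minute of examination and one existing field at the visits concerned, and wording elsewhere. The fit rate may come out slightly lower.

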7.4. Laboratory Procedures

The optical bench will be used to measure the light transmission characteristics for all worn Test lenses. The findings are for internal information only and will not be part of the final report.

8. SUBJECTS COMPLETION/WITHDRAWAL

8.1. Completion Criteria

Subjects are considered to have completed the study if they:

- provided informed consent
- they are eligible
- Completed all required study visits

8.2. Withdrawal/Discontinuation from the Study

A subject will be withdrawn from the study for any of the following reasons:

- Subject death during the study period
- Subject withdrawal of consent
- Subject not compliant to protocol
- Subject lost to follow-up
- Subject no longer meets eligibility criteria (e.g. the subject becomes pregnant)
- Subject develops significant or serious adverse events causing discontinuation of study lens wear
- Subjects who have experienced a Corneal Infiltrative Event (CIE)
- Investigator's clinical judgment regarding the subject safety reasons (that it is in the best interest of the subject to stop treatment)
- Subject missed a scheduled study visit

- Subject not compliant with study lens wear schedule
- Subject not successfully dispensed due to lack of efficacy and safety including poor vision, poor comfort or unacceptable fit
- Subject out of visit window visit with two or more days

For discontinued subjects, the Investigator will:

- Complete the current visit (scheduled or unscheduled)
- Complete the Final Evaluation, indicating the reason that the subject was discontinued from the study
- Record the spherocylindrical refraction with best corrected distance visual acuity
- Collect used test article(s) (worn or brought to the visit) from the subject
- Collect all unused test article(s) from the subject

An additional subject will be enrolled if a subject discontinues from the study prematurely.

In cases where a subject is lost to follow-up, every possible effort must be made to contact the subject and determine the reason for discontinuation/withdrawal. The measures taken to follow up must be documented including two written attempts and a certified letter (or equivalent) as the final attempt.

9. PRE-STUDY AND CONCOMITANT INTERVENTION/MEDICATION

Concomitant medications will be documented during screening and updated during the study. Suspect disallowed oral medications taken for less than one year on a continual (year-round, routine) basis are listed in Section 3.3.1. Document any prescribed or over the counter (OTC) ocular medication currently being taken.

10. DEVIATIONS FROM THE PROTOCOL

Investigator will notify study sponsor upon identification of a protocol deviation. Major protocol deviations must be reported to the sponsor within 24 hours after discovery of the protocol deviation. The Investigator will report deviations per IRB/IEC requirements. All deviations will be tracked and corrective actions implemented as appropriate.

If it becomes necessary for the Investigator to implement a deviation in order to eliminate an immediate hazard to the trial subject, the Investigator may implement the deviation immediately without notification to the sponsor. Within 24 hours after the implemented deviation, the Investigator must notify and provide the rationale to the Sponsor and, as required, the IEC/IRB.

11. STUDY TERMINATION

The occurrence of one or more Unanticipated Serious Adverse Device Effect (USADE), or any SAE where the relationship to study agent cannot be ruled out, may result in stopping further dispensing of test article. In the event of a USADE or SAE, the Sponsor may unmask the treatment

regimen for the subject(s) and will discuss this with the Investigator before any further subjects are enrolled.

The Sponsor will determine when a study will be stopped. The Principal Investigator always has the discretion to initiate stopping the study based on patient safety or if information indicates the study's results are compromised.

JJVCI reserves the right to terminate the study at any time for any reason. Additionally, the IEC/IRB reserves the right to terminate the study if an unreasonable risk is determined. The study can be terminated by the Principal Investigator at the individual clinical site due to specific clinical observations, if in their opinion, after a discussion with JJVCI, it is determined that it would be unwise to continue at the clinical site.

JJVCI (and the IEC/IRB and DMC, if applicable) will evaluate all adverse events. If it is determined that an adverse event presents an unreasonable risk, the investigation, or that part of the investigation presenting the risk, will be terminated, as soon as possible.

Should the study be terminated (either prematurely or as scheduled), the Investigator will notify the IEC/IRB and Regulatory Authority as required by local regulatory requirements.

12. PROCEDURE FOR HANDLING PRODUCT QUALITY COMPLAINTS

A Product Quality Complaint (PQC) refers to any written, electronic, or oral communication that alleges deficiencies related to the identity, quality, durability, reliability, safety, effectiveness or performance of test articles after they have been released for clinical trial use.

Potential complaints may come from a variety of sources including but not limited to subjects, clinical research associates (CRA), clinical operations managers (COM), medical monitors, and site personnel, etc. The following are not considered product quality complaints:

- Subject satisfaction inquiries reported via "Subjective Questionnaires" and "Patient Reported Outcomes (PRO)"
- Clinical test articles that are stored improperly or damaged after receipt at the investigational site
- Lens replacements that occur due to drops/fall-outs
- Damage deemed by clinicians or clinical staff to be caused by handling by the user, and not indicative of a quality deficiency (i.e. tears, rips, etc.), only in situations where there is no deficiency alleged by the subject

Within 24 hours of site personnel becoming aware that a PQC has occurred, the PQC must be recorded in the EDC system, which will trigger an automatic email notification to the appropriate COM/CRA and Clinical QA representative. In cases where the EDC system in use is not configured to send automatic notifications or when an EDC system is not used, the COM/CRA is responsible for notifying Clinical QA upon discovery that a PQC has occurred.

Upon receipt of the EDC notification, the COM/CRA will contact the study site to collect additional information which will include:

- Date the complaint was received/recorded in the EDC System (Date of Sponsor Awareness)
- Who received the complaint
- Study number
- Clinical site information (contact name, site ID, telephone number)
- Lot number(s)
- Unique Subject Identifier(s)
- Indication of who first observed complaint (site personnel or subject)
- OD/OS indication, along with whether the lens was inserted
- Any related AE number if applicable
- Detailed complaint description (scheduled/unscheduled visit, wear time, symptoms, resolution of symptoms, etc.)
- Eye Care Provider objective (slit lamp) findings if applicable
- Confirmation of product availability for return (and tracking information, if available), or rationale if product is not available for return

Once a complaint is received, it will be assessed by the COM, CRA, or trained site personnel to determine if it is an Adverse Event/Serious Adverse Event (AE/SAE). If the complaint results in an AE/SAE, the COM/CRA, or trained site personnel will follow Section 13 of this protocol. If the AE/SAE was potentially the result of a product quality related deficiency, these procedures also applies and will be executed in parallel.

In some cases, a PQC form may be generated in EDC by the site in error. In this event, the PQC forms will be marked "Intentionally Left Blank" or "ILB". Justification for ILB must be documented.

